#### Consent:

Within about 24-48 hours, the ETUDES Assessment & Recruitment Center (ARC) assessors will call an eligible teen to complete informed consent with teen and parent, conduct baseline assessment measures, and onboard the T2C program on the cell phone. A waiver to document consent will be used to obtain consent from parents and assent from minors (12-17 yo) over the phone with the ARC assessor. If a minor participant turns 18 yo during the course of the study, a waiver to document consent will be used to identify if the minor wishes to continue their participation in the study. Date and time of the informed consent & assent phone conversation will be recorded. Prior to this phone call the RA in the primary care practice will have provided the family with a copy of the informed consent wording and HIPAA authorization to review (See recruitment methods section). The ARC assessor will review any areas of concern or question before obtaining family consent and moving on with the Baseline data collection. Consenting will take about 15 minutes.

#### Baseline assessment phone call:

Following the informed consent, the ARC assessor will conduct the baseline assessment measures. The measures include collecting sociodemographic questions, the CSSRS scale & suicide scales, quality of life ratings, treatment history, barriers to treatment, readiness for treatment, attitudes toward seeking psychological help, anxiety & mania adaptive scales via the K-CAT mental health adaptive screen, substance use, depression history, treatment preferences, and if there's a family history of bipolar disorder that impacts the youth's risk for mental health problems. A waiver of HIPAA authorization to collect permission verbally over the phone will be used to access and collect medical record data. Electronic medical record information will be used to supplement treatment and service utilization and uptake of the T2C intervention via the RE-AIM framework described in statistical analysis. Parents will respond to questions about their child, not themselves and youth will answer about themselves. Phone calls will take about 30-60 minutes.

#### Onboarding T2C:

The ARC assessor will use the provided cell phone number on a text-capable device to onboard the T2C program, verify the youth received initial messages, and troubleshoot technological problems with starting the intervention. Upon study entry, the youth will receive a series of welcome messages describing what to expect over the intervention period, expectations for response, and ways to reduce breach of privacy. For example (adolescent): "Welcome to the T2C Program. Over the next week we'll send you daily texts. Set up a password on your phone and erase messages you do not want anyone to see after reading them." We will indicate they can drop out of the T2C program at any time by texting "Quit." [name] has successfully used this onboarding process in prior studies.

#### T2C intervention

Text messages will last for about 1 week and participants will be asked to respond to up to 2 text message queries daily. Psychoeducation will be provided in the form of true/false or multiple choice questions. For example, "True or False: If someone has depression as a teen, they will always have it." To alter false beliefs about treatment, texts will focus on what treatment entails, e.g., "Which of the following happens when you talk to a therapist about depression? (a) They make you tell them all your secrets; (b) They judge you; or (c) they help you understand your

feelings.” Correct responses will be reinforced with a congratulatory message. For incorrect responses, a statement will validate their concern, and then the correct answer will be provided. Questions will be drawn from resources available in the public domain (e.g., SAMHSA). To promote symptom self-monitoring, we will use the single item “How often have you felt down, depressed or sad today on a scale 1 (not at all) to 5 (all day)? To decrease stigma, we will use cognitive bias modification strategies used successfully in prior research. Specifically, T2C will present individuals with a series of text statements regarding beliefs about using MH services (e.g., “Seeing a therapist means that I am weak”). Individuals can select “true” or “false” in response to each statement. Incorrect responses (i.e., indicating help-seeking stigma) are followed by corrective feedback (i.e., the correct answer); correct responses (i.e., promoting help seeking) are positively reinforced. Individuals repeat these tasks to facilitate internalization of more adaptive cognitions, consistent with cognitive therapy principles. T2C will send adolescents communication prompts weekly (or as requested when teens voluntarily check their self-reported mood ratings) to discuss ongoing mood symptoms with their parent, e.g., “Try to talk with your parent about these symptoms.”

**T2C for Parents:** Parent subjects will receive similar psychoeducation and cognitive bias modification about depression/suicidality and MH treatment about their child, except focused on typical parental cognitive barriers. Tailoring is the method of personalizing characteristics of an intervention (e.g., content, timing) to maximize receptivity and engagement. Tailoring within digital interventions has been shown to be an important to optimize effectiveness. In T2C, intervention material will be tailored to adolescents’ and parents’ baseline characteristics; based on characterization, we will prioritize specific T2C intervention material. The tailoring will occur based on the text responses the parent offers about their child, not their personal characteristics about attending treatment for themselves.

#### Follow Up assessment phone calls:

During each follow up assessment phone call during week 4 and week 12 following the baseline phone call and onboarding to T2C, the ARC assessor will update demographic & contact information, ascertain continuing consent and assent to participate in study, and collect measures on depression, anxiety, mania, and suicide symptoms, the CSSRS, quality of life ratings, barriers to treatment, readiness for treatment, depression literacy, treatment utilization and history since last assessment, substance use, and additionally information on client satisfaction and usability processes with the T2C intervention once the family has completed the program. The youth will respond to questions about themselves and the parent about their child. Phone calls will take about 30-60 minutes.

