## Study Objectives

To increase rates of MH care initiation, we propose an automated TM intervention, “Text to Connect” (T2C), that aims to increase motivations in at-risk adolescents and their parents. We will develop and examine T2C using dissemination and implementation science principles, specifically, the RE-AIM framework, for balancing internal and external validity and optimizing uptake and sustainability. We will select the most salient of the following behavior change techniques: psychoeducation, cued mood monitoring, adolescent-parent communication prompts, cognitive bias modification, and cues to action. Intervention material will be tailored to baseline characteristics. We will begin with treatment development. In an initial usability phase, we will develop and iteratively refine the format and content of T2C based on feedback from stakeholders. Data will inform a subsequent feasibility trial comparing T2C with treatment as usual (TAU) using a stepped wedge design.

Aim 1 (Phase 1, Development). To develop T2C, a TM intervention to address motivational barriers to MH treatment initiation for depression and/or suicidal screen-positive adolescents and parents in pediatric primary care. We will collaborate with NuRelm and the Office of Academic Computing at WPIC and the Methods Core to develop T2C based on stakeholder feedback (adolescents, parents, pediatricians, MH clinicians).

Aim 1b (Phase 1b, Feasibility). To examine the feasibility of T2C in pediatric primary care clinics (n=2 clinics, 50 adolescents) using a stepped wedge design.

Hypothesis 1b: Readiness for MH care will be greater among adolescents in T2C vs adolescents referred during TAU. We will first conduct t tests for continuous variables and chi square tests for categorical variables to examine for baseline differences in demographic

and clinical variables. We will use generalized linear mixed models (nesting for site) to examine for between-intervention differences in readiness. Baseline characteristics that distinguish the groups will be included as covariates in models examining treatment effects.

Aim 2: Explore differential rates of service utilization (behavioral and physical health services) among youth who receive Text2Connect (T2C) versus Treatment As Usual (TAU).

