## **Statistical Considerations**

A stepped wedge design was selected for both ethical considerations and feasibility. A stepped wedge cluster randomized trial design involves the sequential random rollout of an intervention over multiple time periods following a “baseline” period when no cluster has been exposed. The

crossover is typically in one direction, from control to intervention, and continues until all of the clusters receive the intervention with observations taken from every cluster and at each time period. All 3 studies in the ETUDES Center, and specifically, T2C, will utilize this design. Prior to study start, each CCP study practice will be randomly assigned to switch from Treatment As Usual (TAU) to the intervention.

In the proposed stepped wedge design, all practices start with TAU (i.e., PCP referral to embedded MH care) and are randomized to transition to implement T2C at different times. All clinics will be initially monitored for at least 2 months during TAU, followed by a staggered adoption of T2C. During each time period, a new clinic will begin to use T2C (order determined by block randomization. A web-based system will randomly assign the next clinic to begin.

With regard to Hypothesis 1: We will conduct t tests for continuous variables and chi square tests for categorical variables to examine for baseline differences in demographic and clinical variables. We will use generalized linear mixed models (nesting for site) to examine for between-intervention differences in readiness. Baseline characteristics that distinguish the groups will be included as covariates in models examining treatment effects.

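### Baseline readiness should always be a covariate in the Hypothesis 1b comparison, not left to a test of baseline differences; the main readiness visit should be named in the same edit

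*Combined protocol and SAP*

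**What the plan says.** Hypothesis 1b (Study Objectives) reads: "Readiness for MH care will be greater among adolescents in T2C vs adolescents referred during TAU". It names no visit, change score or instrument.

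Readiness is measured three times on each youth. The section Baseline assessment phone call lists "treatment history, barriers to treatment, readiness for treatment, attitudes toward seeking psychological help". The section Follow Up assessment phone calls sets two later calls, "During each follow up assessment phone call during week 4 and week 12 following the baseline phone call and onboarding to T2C", and lists among their content "barriers to treatment, readiness for treatment, depression literacy, treatment utilization and history since last assessment".

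The analysis appears in Study Objectives and, in nearly the same words, in Statistical Considerations. It has three steps:

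- Screening: "We will conduct t tests for continuous variables and chi square tests for categorical variables to examine for baseline differences in demographic and clinical variables".
- Model: "We will use generalized linear mixed models (nesting for site) to examine for between-intervention differences in readiness".
- Covariates: "Baseline characteristics that distinguish the groups will be included as covariates in models examining treatment effects".

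No cutoff is given for the screening tests. Baseline readiness is not named as a covariate, and it is not explicit that it counts among the demographic and clinical variables to be screened. The size of this phase is given in Aim 1b: "To examine the feasibility of T2C in pediatric primary care clinics (n=2 clinics, 50 adolescents) using a stepped wedge design". No alpha, power, effect size, SD or within-youth correlation is stated.

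**The concern.** The baseline value of an outcome is usually among its strongest predictors, and here it is already collected. The stated rule makes its use depend on a chance or period difference between the groups, whereas its value as a covariate depends on its correlation with follow-up readiness. When the groups look alike, the rule leaves it out, and the variance it would have explained stays in the error term. With 50 adolescents, that loss can be material to the width of the interval for T2C against treatment as usual.

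Two smaller gaps sit beside it. The hypothesis does not say whether week 4, week 12 or both will be analysed, and the model description writes no youth or visit term for the case where both are used. These are missing details that the same edit can close.

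**Working it through.** **Inputs from the documents.** 2 clinics and 50 adolescents (Study Objectives); readiness at baseline, week 4 and week 12 (the two assessment-call sections); a mixed model with a site term and covariates chosen by baseline tests (Statistical Considerations). The plan states no figure on this point, so there is none to reproduce.

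**Assumptions, because the documents give no values.** Split 25/25, SD 1, continuous score, one follow-up visit, complete data, groups alike at baseline, screening cutoff p<0.05, baseline-to-follow-up correlation r of 0.3 to 0.8, and no calendar trend.

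**Step 1: how often the rule admits baseline readiness.** With groups alike, a test at 0.05 flags a difference in 5% of trials. Simulation (40,000 runs, site fixed) gave 5.0%.

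**Step 2: large-sample SD of the estimate.**

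- Unadjusted: s = sqrt(2/25) = 0.283.
- Always adjusted: s × sqrt(1 − r²).
- Under the rule, the covariate is omitted only when the standardised baseline difference Z lies within ±1.96. The part of the variance of Z then left in the estimate is 0.95 − 2 × 1.96 × φ(1.96) = 0.95 − 0.229 = 0.721, where φ is the standard normal density. The SD is therefore s × sqrt(1 − r² + 0.721r²) = s × sqrt(1 − 0.279r²).

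**Step 3: numbers, in outcome SDs.**

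| r | Rule, formula | Always, formula | Reduction | Rule, simulated | Always, simulated | Reduction |
|---|---|---|---|---|---|---|
| 0.3 | 0.279 | 0.270 | 3% | 0.281 | 0.273 | 3% |
| 0.5 | 0.273 | 0.245 | 10% | 0.276 | 0.249 | 10% |
| 0.7 | 0.263 | 0.202 | 23% | 0.264 | 0.204 | 23% |
| 0.8 | 0.256 | 0.170 | 34% | 0.258 | 0.172 | 33% |

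For example, at r = 0.5 the simulated reduction is 1 − 0.249/0.276 = 0.098. Formula and simulation agree to within one percentage point.

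**Step 4: false positives under the rule.** The simulated type I error is 4.8% at r = 0.3, falling to 3.2% at r = 0.8. The rule is slightly conservative.

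**Step 5: if baseline readiness is not screened at all.** It would then never enter. Always adjusting would cut the variance by r², which is 9%, 25%, 49% and 64%, so the SD falls by 1 − sqrt(1 − r²), which is 5%, 13%, 29% and 40%.

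**Scenario only: what the unwritten visit structure could do.** The plan does not say that visits will be pooled. With within-youth correlation rho and two-sided alpha of 5%:

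- Both follow-ups as outcomes, no youth term and no baseline adjustment: the true SE is sqrt(1 + rho) times the reported SE, and type I error is 2 × (1 − Φ(1.96/sqrt(1 + rho))) = 8.6%, 11.0%, 13.3% and 14.4% for rho 0.3, 0.5, 0.7 and 0.8.
- Baseline also entered as an outcome, condition by time tested, no youth term: per youth, the mean of the two follow-ups minus baseline has variance (1 + rho)/2 + 1 − 2rho = 1.5(1 − rho), against 1.5 if the values are taken as independent. The true SE is sqrt(1 − rho) times the reported SE, and type I error is 1.9% at rho 0.3 and 0.6% at rho 0.5.

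The direction of the error therefore depends on a layout that the plan does not give.

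**The case against.** A reader might infer that the plan will pool weeks 4 and 12 in a site-only model and so report a standard error that is too small. The documents do not support this. No section says the visits will be pooled, or that one will be chosen after both are seen. Nesting for site can mean youths nested within sites. As shown above, the error would reverse under another layout that the plan equally allows, and one visit named in advance would carry no error from this source. This objection stands in full, so the type I figures remain a scenario.

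Against the covariate point itself, four things can be said:

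- The plan says which covariates will be included; it does not bar others, so adjustment for baseline readiness is not excluded.
- The 5% inclusion figure needs groups alike at baseline and a cutoff of p<0.05. Under the stepped-wedge rollout, T2C and usual-care youths come from different calendar periods, so likeness is not assured.
- The reductions assume a continuous score. The plan names no instrument and specifies generalized models, so a categorical readiness measure need not gain as much.
- The upper end, 33%, needs a correlation of 0.8, for which the documents give no support.

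These points limit the size of the gain, and each is carried as a condition in the verdict. They do not defend the rule: none gives a reason to leave the use of a collected baseline outcome to a test of group difference.

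**Conclusion.** The point holds as an inexpensive improvement in precision. As written, the covariate rule would usually leave baseline readiness out if the groups are alike at baseline and the cutoff is p<0.05. Under the assumptions listed, always including it lowers the SD of the T2C estimate by about 3% (r = 0.3) to 33% (r = 0.8). The benefit shrinks with weaker correlation, and the figures do not cover missing data or a categorical score. No inflation of false positives is claimed for the rule.

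The unnamed visit and the unwritten youth term are omissions to close. They do not show that the planned analysis is invalid. The practical consequence is limited: this is a feasibility phase with two clinics and no alpha or power attached to the readiness comparison. Handling of calendar period in the stepped-wedge model is a separate matter and is not settled here.

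**What to change.** Edit the analysis text in both Study Objectives and Statistical Considerations:

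1. State that baseline readiness is always a covariate in the Hypothesis 1b model, whether or not it differs between groups.
2. Name week 4 or week 12 as the main readiness visit, at the sponsor's choice, and label the other secondary.
3. If both visits are modelled, write a participant random intercept or a within-youth covariance, together with a visit term. If nesting for site was meant to include youths within sites, say so.

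The cost is one degree of freedom for baseline readiness, one visit labelled secondary, and wording in two sections. No new data or calls are needed. These are additions to the site term and not a full stepped-wedge specification.

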In order to enhance uptake of T2C, we will conduct the proposed work within the RE-AIM framework, as follows. (R)each: The percentage and characteristics of screen-positive adolescents referred for MH treatment who are offered, and agree to participate in, T2C. (E)fficacy: The impact of T2C on MH treatment initiation and engagement. (A)doption: The percentage and characteristics of PCPs who refer to T2C upon making a referral for MH care for a screen-positive adolescent. (I)mplementation: The percentage and characteristics of patients who consent to T2C who complete the TM intervention. (M)aintenance: The percentage and characteristics of PCPs who recommend T2C to appropriate patients upon long-term follow-up, as well as T2C utilization by referred adolescents/parents via de-identified data. The baseline and follow up measures administered are mapped onto each component of the RE-AIM framework.

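### Read literally, the plan asks only families who completed T2C about satisfaction and usability, so the ratings may be too favourable

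*Combined protocol and SAP*

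**What the plan says.** All references are to the Combined protocol and SAP.

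- **Follow Up assessment phone calls.** The calls are timed thus: "During each follow up assessment phone call during week 4 and week 12 following the baseline phone call and onboarding to T2C". The section lists the measures for each call, readiness among them, and then adds "client satisfaction and usability processes with the T2C intervention once the family has completed the program". No other measure in the list carries a completion condition. The same section has the assessor "ascertain continuing consent and assent to participate in study" at each call.
- **Onboarding T2C.** Youths are told "they can drop out of the T2C program at any time by texting" the word Quit.
- **T2C intervention.** "Text messages will last for about 1 week".
- **Statistical Considerations (RE-AIM).** Implementation is defined as "The percentage and characteristics of patients who consent to T2C who complete the TM intervention". Reach is defined as "The percentage and characteristics of screen-positive adolescents referred for MH treatment who are offered, and agree to participate in, T2C".
- **Study Objectives.** Aim 1b is "To examine the feasibility of T2C in pediatric primary care clinics", with 2 clinics and 50 adolescents. Its hypothesis concerns readiness.

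No section says whether families who leave T2C early are asked about satisfaction or usability. No exit questionnaire is described, and no target or analysis is given for these data.

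**The concern.** Satisfaction and usability ratings are most informative when they include the people who did not like the product. If the questions go only to families who finished, the respondents have selected themselves by persisting, and those with most to say about why T2C did not suit them are missing. Their ratings would probably be lower than those of completers, so a completers-only summary would probably be too favourable. The sponsor would also lose the reasons for stopping, which is what a team refining a text program from stakeholder feedback would want to know.

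**Working it through.** The plan states no figure on this point, so there is nothing to reproduce. The check has two parts: what the wording does, and how large the effect could be.

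**1. Timing note or condition on who is asked?** The texts run for about 1 week and the first call is at week 4, roughly 4 − 1 = 3 weeks after the texts end. The program period is therefore over for every T2C family at both calls. As a timing note, the phrase rules out neither call and adds little. It has a clear effect only if it decides who is asked.

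**2. Does a family that quits count as having completed?** The Implementation measure treats completion as a status that some consenting patients do not reach, and the onboarding section describes texting Quit as dropping out of the program. On the document's own usage, a youth who quits has not completed. The condition is also attached to the family, so one member's stopping could remove both the youth's and the parent's ratings.

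**3. Possible size (illustration; every input is assumed).** Let q be the share of families who stop, Sc the share satisfied among completers, and Sq the share satisfied among those who stopped.

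- Share satisfied among all onboarded = (1 − q) × Sc + q × Sq
- Excess of the completers-only figure = Sc − that share = q × (Sc − Sq)

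Example with Sc = 80%, q = 20%, Sq = 30%: 0.80 × 0.80 + 0.20 × 0.30 = 0.70, an excess of 10 points. The range with Sc = 80%, in percentage points:

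| q | Sq = 80% | Sq = 60% | Sq = 30% | Sq = 0% |
|---|---|---|---|---|
| 10% | 0 | 2 | 5 | 8 |
| 20% | 0 | 4 | 10 | 16 |
| 30% | 0 | 6 | 15 | 24 |
| 40% | 0 | 8 | 20 | 32 |

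The split of the 50 adolescents between TAU and T2C is not stated. If 25 received T2C, 10% to 40% stopping would be 2.5 to 10 youths.

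**4. Can the completion rate repair this afterwards?** Only as a bound. If q is known but Sq is not, the all-onboarded share lies between (1 − q) × Sc and (1 − q) × Sc + q. With Sc = 80% and q = 20%, that is 0.64 to 0.84, an interval as wide as q itself.

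**5. Against sampling error.** With an assumed 20 completers and 80% satisfied, the approximate 95% margin is 1.96 × √(0.80 × 0.20 / 20) = 1.96 × 0.0894 = 0.175, or about 17.5 points.

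**The case against.** The strongest reply is that the phrase may mean no more than asking about T2C after T2C is over, or may only separate T2C families from TAU families, who have no program to rate. The documents do not exclude either reading. A reader might infer that quitters are definitely left out and that the ratings are definitely inflated. The text does not go that far: it leaves assessors without an instruction for these families, and its literal sense points to omission.

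It is also fair to say that stopping is not hidden. Implementation keeps non-completers in its denominator and Reach counts those who decline, both with their characteristics. That stands, but these measures show how many stopped or refused and who they were, not what they thought of T2C or why they left.

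Two stronger inferences fail.

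- A reader might conclude that the readiness comparison is biased as well. Readiness is collected at each call with no completion condition, Quit is described as leaving the program and not the study, and study consent is checked separately. Nothing in the text removes quitters from follow-up or from the T2C group.
- A reader might treat acceptability as a core output. The aim is worded as feasibility, the hypothesis concerns readiness, and no acceptability endpoint, threshold or decision rule is defined.

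Finally, in a study this small, sampling error on a satisfaction percentage may be as large as the bias or larger. That limits how much weight the figure can bear. It is no reason to keep an avoidable selection in how the figure is collected.

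**Conclusion.** The point holds in a limited form. As worded, the rule selects completers for satisfaction and usability, and the ratings may be too favourable as a result. The amount cannot be estimated from the documents. On the assumed grid it runs from 0 to 32 points. The upper end needs 40% stopping with none of them satisfied. The excess is zero if nobody stops, if those who stop are equally satisfied, or if assessors ask them anyway. The direction rests on the assumption, reasonable but untested here, that those who stop are less satisfied than those who finish.

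What is affected is a descriptive measure in a feasibility study. No stated hypothesis or decision turns on it. The case for changing the wording is that the change is cheap and useful under either reading.

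**What to change.** In Follow Up assessment phone calls, replace the completion condition with a statement that satisfaction and usability are collected at the scheduled week-4 and week-12 calls from every family onboarded to T2C, whether or not they completed it, including those who texted Quit or stopped replying. Have the assessor record the reason for stopping.

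In Statistical Considerations, add that these results are reported for all onboarded families and then by completion status, with the number who answered in each group. Completion should be defined there too, since the documents give no criterion for it.

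If it is what the sponsor intends, a sentence saying that Quit ends the texts only, and not study follow-up, would be a helpful clarification. It does not correct an error.

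The cost is a few sentences, as the calls are already scheduled. The drawback is that some families who stopped will decline to answer, so the all-onboarded figure will still have gaps. Showing the response count by completion status lets a reader judge them.
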